7.1.2 Oocyte Retrieval and Blastocyst Transfer

Information regarding the total number of oocytes retrieved, the number of mature oocytes obtained, number of oocytes undergoing ICSI, and number of fertilized (2PN) oocytes will be documented in the eCRF. Blastocyst transfer cycle data will be collected and documented in the eCRF including: endometrial thickness in mm, grade of blastocyst transferred, and presence of blood or mucus within the catheter tip after transfer is completed.

7.1.3 Transvaginal Ultrasounds

Transvaginal ultrasounds (including ovaries, adnexa, endometrial thickness in mm, follicular development - diameter of each follicle in mm, hyper- or hypo-echogenicity will be documented and recorded in the eCRF), and if pregnant, presence of intrauterine gestational sac, fetal pole, and/or fetal heartbeat, will be collected. Other ultrasounds may be performed throughout the ICSI treatment per standard practice but will not be documented in the eCRF.

7.1.4 Central Laboratory Tests

The following laboratory tests will be performed by a central laboratory:

- Screening and EOT Visit: serum chemistry: non-fasting glucose, blood urea nitrogen, creatinine, potassium, sodium, chloride, calcium, aspartate aminotransferase, alanine aminotransferase, and gamma-glutamyl transferase.
- Screening and EOT Visit: hematology: red blood cell count, white blood cell count, hematocrit, hemoglobin, platelet count, and differential count.
- Screening: AMH (all subjects will have an AMH sample taken). This must be at least 3 months after the cessation of any hormonal birth control and may be repeated 1 additional time to determine eligibility.

Trial Code: 000205

Date: 10 Dec 2015

E-Protocol Amendment-19588; Ver. 1.0

Supersedes: 28 October 2015

Page 38 of 69

- Day 1, Day 6, final day of stimulation: FSH, hCG, LH, androstenedione, total testosterone, and DHEA.
- Day 1, Day 6, final day of stimulation, and Visit 4 (in the morning following hCG administration): E2, P4.

The Investigator will review the laboratory results and evaluate and document whether the results are normal or abnormal and whether or not abnormal results are clinically significant. The laboratory report will be signed and dated by the Investigator.

7.1.5 Local Laboratory Tests

The following laboratory tests will be performed at each site's local or reference laboratory per standard practice and will be reviewed by the Investigator. All blood draws should be non-fasting. The results must be available and documented in the subject's chart and eCRF (if applicable).

- Hormones: total testosterone, prolactin, and TSH should be drawn at screening or within 12 months prior to screening and documented to be within normal limits or considered not clinically significant by the investigator. Early follicular phase (Day 2/3) serum levels of FSH should be documented between 1- 12 IU/L (inclusive) at screening or in the preceding 6 months prior to screening.
- Other laboratory assessments: negative serum hepatitis B surface antigen, hepatitis C antibody, HIV antibody, and rapid plasma reagin tests are to be done at screening or within 6 months prior to screening and documented to be within normal limits.
- FSH (cycle Day 2-3) within 6 months of screening.
- E2, P4, LH, and serum β-hCG tests collected at various time points during stimulation and luteal support.

7.1.6 Ovarian Hyperstimulation Syndrome Monitoring

In women undergoing COS, an excessive response to follicular stimulating agents may lead to the development of OHSS, which has a spectrum that can be categorized as mild, moderate, or severe. If OHSS is suspected, the subject should have a TVUS to document ovarian size and presence of ascites, as well as serum chemistry and hematology (see screening laboratories).

Trial Code: 000205

Date: 10 Dec 2015

E-Protocol Amendment-19588; Ver. 1.0

Supersedes: 28 October 2015

Supersedes: 28 October 2015 Page 39 of 69

Table 2 Classification of Mild, Moderate, and Severe OHSS

Mild OHSS	Grade 1: Abdominal distension and discomfort	
	Grade 2: Features of Grade 1 plus nausea/vomiting and/or diarrhea. Ovaries enlarged to 5-12 cm. ¹	
Moderate OHSS	Grade 3: Features of mild OHSS plus ultrasonic evidence of ascites. ²	
Severe OHSS	Grade 4: Features of moderate OHSS plus clinical evidence of ascites and/or hydrothorax (or breathing difficulties). Paracentesis due to OHSS symptoms. ³	
	Grade 5 All of the above plus change in blood volume, increased blood viscosity due to hemoconcentration, coagulation abnormalities, and diminished renal perfusion and function. ⁴ Hospitalization due to OHSS symptoms.	

- 1. For each ovary, the size will be the average of the greatest diameter and its greatest perpendicular diameter. Ovarian enlargement will be based on the average size of the right and left ovaries. The sizes of both ovaries should be recorded.
- 2. For subjects with transvaginal evidence of ascites, the size of the fluid pockets in the pelvis (Douglas pouch, vesicouterine pouch, etc.) should be estimated by measuring the greatest diameter and its greatest perpendicular diameter, and multiplying these 2 numbers (the unit will be cm²). Peritoneal fluid is the total size of all fluid pockets in the pelvis.
- 3. In case of paracentesis, the volume of fluid drained should be measured.
- 4. Hemoconcentration is defined as hematocrit >45 %. Electrolyte disturbances are defined as hyponatremia (sodium <135 mEq/L) and/or hyperkalemia (potassium >5.0 mEq/L). Coagulation abnormalities are defined as presence of thromboembolic events, abnormal prothrombin time, or abnormal activated partial thrombin time. Diminished renal perfusion is defined as creatinine >1.2 mg/dL. Oliguria is defined as urine output less than 500 mL/24 hours. Anuria is defined as failure to produce urine. If applicable, actual volume of urine output will be recorded.

All cases of OHSS will be considered AEs and will be recorded in the source documents for that subject and on the AE page in the eCRF. Severe OHSS that requires medical or surgical intervention (i.e., paracentesis or hospitalization) is considered an SAE (see Section 8.4).

Early OHSS is defined as OHSS with onset ≤ 9 days after triggering of final follicular maturation. Classification of grade is according to Golan's classification system (Golan, 1989) and all OHSS cases will be graded as mild, moderate, or severe. Preventive interventions for early OHSS cover cycle cancellation due to excessive ovarian response, triggering of final follicular maturation with GnRH agonist, and administration of dopamine agonist (the latter is only considered as preventive intervention in subjects with ≥ 20 follicles of ≥ 12 mm).

Late OHSS is defined as OHSS with onset >9 days after triggering of final follicular maturation.

7.1.7 Concomitant Medications

At each study visit, subjects will be queried regarding use of any medication other than study drug since the last visit. Any use of prior medication or concomitant medication will be recorded in the source documents and eCRF and include the following information: name of medication, total daily dose, route of administration, start and stop dates, and reason for use. If the reason for the use of concomitant medication meets the definition of an AE, the AE should be recorded in the source documents for that subject and on the AE page in the eCRF.

E-Protocol Amendment-19588; Ver. 1.0 Supersedes: 28 October 2015 Page 40 of 69

Date: 10 Dec 2015

7.2 Other Assessments

7.2.1 Physical and Gynecological Examinations

A complete physical and gynecological examination will be performed at screening (including height, weight, BMI calculation, and pelvic and breast examinations). In addition, a Pap smear will be performed at screening if not done in the previous 24 months. If done in the previous 24 months, a copy of the report must be filed in the subject's chart.

7.2.2 Medical History/Menstrual History

A complete medical and gynecological history will be obtained at screening and will include a review of prior medical history, menstrual history, concurrent conditions by body system, history of alcohol, tobacco, and drug use, and female reproductive status. Medical history findings will be recorded in the subject's chart and eCRF.

7.2.3 Vital Signs

Blood pressure, heart rate, and temperature will be measured at screening. Blood pressure and heart rate are to be measured while the subject is seated under resting conditions.

7.2.4 Number of Oocytes Retrieved

The number of oocytes retrieved will be recorded at the oocyte retrieval visit.

7.2.5 Metaphase II Oocytes

Maturity stage will be assessed prior to undergoing ICSI. Maturity stage will be categorized as germinal vesicle, metaphase I, metaphase II, degenerated, or other.

7.2.6 Fertilization Rate

The number of pronuclei will be counted on Day 1 post-insemination and recorded. Fertilization rate is the number of 2PN oocytes divided by the number of oocytes retrieved.

7.2.7 Number and Quality of Embryos on Day 3

Each embryo will be evaluated on Day 3 post-insemination. The quality evaluation will consist of assessment of cleavage stage and embryo morphology parameters (blastomere uniformity, cell size, degree of fragmentation, and visual signs of multinucleation).

Cleavage stage will be defined by the number of blastomeres.

Blastomere uniformity will be classified as equally sized blastomeres or unequally sized blastomeres (largest blastomere >25% larger in average diameter compared to the smallest blastomere).

Cell size will be classified as stage-specific cell size or not stage-specific cell size.

Trial Code: 000205

Date: 10 Dec 2015

E-Protocol Amendment-19588; Ver. 1.0

Supersedes: 28 October 2015

Page 41 of 69

Degree of fragmentation will be classified as 1 of the following: 0%, 1-10%, 11-20%, 21-25%, 26-30%, 31-50%, or >50% fragmentation, or totally fragmented (no blastomeres recognized).

Visual sign of multinucleation will be evaluated as a yes or no.

7.2.8 Number and Quality of Blastocysts on Day 5

Blastocyst Expansion and Hatching Status, Blastocyst Inner Cell Mass Grading, and Trophectoderm Grading

The quality evaluation of blastocysts on Day 5 after oocyte retrieval will consist of assessment of 3 parameters: blastocyst expansion and hatching status, blastocyst inner cell mass grading, and trophectoderm grading. The scoring is based on the classification system by Gardner & Schoolcraft, 1999, with the addition of D-categories for inner cell mass and trophectoderm.

Blastocyst expansion and hatching status will be assessed as 1 of the following:

- 1: An early blastocyst, blastocoel being less than half volume of that of the embryo.
- 2: A blastocyst with a blastocoel whose volume is half of, or greater than half of, that of the embryo.
- 3: A blastocyst with a blastocoel completely filling the embryo.
- 4: An expanded blastocyst with a blastocoel volume larger than that of the early embryo, with a thinning zona.
- 5: A hatching blastocyst with the trophectoderm starting to herniate through the zona.
- 6: A hatched blastocyst, in which the blastocyst has completely escaped from the zona.

For blastocysts with expansion and hatching status 3-6, blastocyst inner cell mass grading and trophectoderm grading will be evaluated.

Blastocyst inner cell mass grading will be assessed as 1 of the following:

- A: Tightly packed, many cells.
- B: Loosely grouped, several cells.
- C: Very few cells.
- D: Degenerative or no inner cell mass.

Trophectoderm grading will be assessed as 1 of the following:

- A: Many cells forming a cohesive epithelium.
- B: Few cells forming a loose epithelium.
- C: Very few, large cells.
- D: Degenerative or very large cells.

Date: 10 Dec 2015 E-Protocol Amendment-19588; Ver. 1.0 Supersedes: 28 October 2015 Page 42 of 69

Blastocysts with expansion and hatching status 3-6 will have a score combining the 3 parameters (blastocyst expansion and hatching status, inner cell mass, and trophectoderm); e.g., 4AB for a blastocyst with blastocyst expansion and hatching status 4, inner cell mass grading A, and trophectoderm grading B.

Trial Code: 000205

7.2.9 Overall Blastocyst Quality on Day 5

The overall blastocyst quality on Day 5 is based on the blastocyst expansion and hatching status, inner cell mass grading, and trophectoderm grading.

Excellent-quality blastocysts are defined as those with blastocyst expansion and hatching status 4, 5, or 6, inner cell mass grading A, and trophectoderm grading A or B. The number and percentage of excellent-quality blastocysts on Day 5 is a secondary endpoint. This will be based on the best overall quality score of the Day 5 post-insemination assessments.

Good-quality blastocysts are defined as those with blastocyst expansion and hatching status 3, 4, 5, or 6, inner cell mass grading B, and trophectoderm grading A or B. The number and percentage of good-quality blastocysts on Day 5 will be based on the best overall quality score. The number and percentage of excellent-quality blastocysts and good-quality blastocysts on Day 5 will be calculated. The best blastocyst based on Day 5 morphology will be transferred.

All expanded blastocysts with Blastocyst Expansion and Hatching Status 3-6, Inner Cell Mass grading A or B, and Trophoectoderm Grading A, B, or C. should be biopsied.

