7.2.10 Compaction Assessment in Morulas

Embryos that have not reached the blastocyst stage on Day 5, but are morulas, will also be evaluated. Morulas will be categorized as 1 of the following 3 options:

- Compacted: complete compaction. Tightly compacted cells. Individual cell membranes are no longer visible.
- Compacting: early stage. Cells can be distinguished.

Abnormal compaction: regional or partial compaction, or few cells (<8) in compaction

Day 5 morulas may be considered for extended culture as per the investigator/site standard of care. Day 6 or Day 7 viable blastocysts can then undergo trophectoderm biopsy and vitrification. All expanded blastocysts with Blastocyst Expansion and Hatching Status 3-6, Inner Cell Mass grading A or B, and Trophoectoderm Grading A, B, or C. should be biopsied.

The quality of Day 6 or Day 7 embryos should be assessed and recorded on the eCRF according to the criteria specified in section 7.2.9.

Date: 10 Dec 2015 E-Protocol Amendment-19588; Ver. 1.0 Supersedes: 28 October 2015 Page 43 of 69

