- The quality of blastocysts 5 days after oocyte retrieval will be assessed by blastocyst expansion and hatching status, blastocyst inner cell mass grading, and trophectoderm grading. Frequency distributions will be provided for each treatment group at the blastocyst level.
- The best quality blastocyst 5 days after oocyte retrieval at the subject level will be summarized for excellent-quality blastocysts and good-quality blastocysts separately by treatment using descriptive statistics.
- The aneuploidy rate will be expressed as a percentage for each subject and calculated as 100 times the ratio of the number of aneuploid blastocysts to the total number of blastocysts. Descriptive statistics will be provided by treatment group.

Date: 10 Dec 2015 E-Protocol Amendment-19588; Ver. 1.0 Supersedes: 28 October 2015 Page 54 of 69

• Endometrial thickness and the echogenicity pattern will be summarized by frequency distribution and by descriptive statistics, as appropriate, for each treatment group at stimulation Day 6, the last day of stimulation, and at the time of blastocyst transfer in the fresh cycle.

Trial Code: 000205

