9.3.9 Quality of Blastocysts 5 Days after Oocyte Retrieval

The quality of blastocysts 5 days after oocyte retrieval will be assessed by blastocyst expansion and hatching status, blastocyst inner cell mass grading, and trophectoderm grading. Blastocyst information collected on day 6 and 7 will be summarized similarly. Furthermore, the overall quality of the blastocysts on day 5 will also be summarized. Frequency distributions will be provided for each treatment group at the blastocyst level.

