9.3.10 Best Quality Blastocysts 5 Days after Oocyte Retrieval

The best quality blastocyst 5 days after oocyte retrieval at the subject level will be summarized for excellent-quality blastocysts and good-quality blastocysts separately by treatment using descriptive statistics.

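### Protocol 7.2.9 leaves blastocysts graded 3AA and 3AB out of both quality classes while the lower-graded 3BB counts as good, so the good-quality summaries do not follow the grades

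*Protocol*

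**What the plan says.** Protocol 7.2.8 gives every blastocyst at expansion 3 to 6 an inner cell mass grade and a trophectoderm grade, each from A to D. Protocol 7.2.9 then forms two overall classes.

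- Excellent: "expansion and hatching status 4, 5, or 6, inner cell mass grading A, and trophectoderm grading A or B".
- Good: "Good-quality blastocysts are defined as those with blastocyst expansion and hatching status 3, 4, 5, or 6, inner cell mass grading B", again with trophectoderm A or B.

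On the counting, 7.2.9 adds: "The number and percentage of good-quality blastocysts on Day 5 will be based on the best overall quality score". It does not say how scores are ranked to find the best one.

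The classes are used in these places:

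- Protocol 9.6.3 and SAP 9.3.10: each woman's best Day 5 blastocyst is "summarized for excellent-quality blastocysts and good-quality blastocysts separately by treatment".
- SAP 9.3.9: "Furthermore, the overall quality of the blastocysts on day 5 will also be summarized". No levels are given.
- Protocol 7.2.10: Day 6 and Day 7 embryos "should be assessed and recorded on the eCRF according to the criteria specified in section 7.2.9".

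SAP 9.2.1 also breaks the ongoing pregnancy rate down by the quality of the transferred blastocyst, without naming levels. Neither the SAP sections that use the classes nor SAP section 12 restates or changes them.

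**The concern.** A score that falls in neither class is not in itself a fault, since most scores do. The fault is that two unclassified scores are better, on the protocol's own scales, than scores counted as good. The class labels then stop following the grades.

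Embryo quality is a stated secondary objective and Day 5 blastocyst quality a listed secondary endpoint. If stimulation in one arm moved blastocysts from 3BB to 3AA, that arm would lose one good-quality blastocyst for each such shift and gain nothing in the excellent column. An improvement would be reported as a deterioration. At subject level, a woman whose best blastocyst is 3AA appears in neither category of SAP 9.3.10, while a woman whose best is 3BB appears as good.

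**Working it through.** **Inputs.** Scores: expansion 3, 4, 5, 6; inner cell mass A to D; trophectoderm A to D (Protocol 7.2.8). Classes: Protocol 7.2.9, applied literally. The plan gives no count of its own to reproduce.

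**Direction of the scales.** The grade descriptions run from many, well-organised cells (A) down to degenerative or absent tissue (D). A is therefore better than B on both letter scales, which fits with excellent requiring inner cell mass A. A higher expansion number is taken as better; this assumption is not needed for the three pairs found below, because all of them lie within expansion 3.

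**Counts under the current rule.**

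- All scores: 4 × 4 × 4 = 64.
- Excellent: 3 × 1 × 2 = 6 (4AA, 4AB, 5AA, 5AB, 6AA, 6AB).
- Good: 4 × 1 × 2 = 8 (3BA, 3BB, 4BA, 4BB, 5BA, 5BB, 6BA, 6BB).
- Neither: 64 − 6 − 8 = 50.

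**Inverted pairs.** Call a pair inverted if one score is at least as good on all three scales and better on at least one, yet sits in a lower class (excellent above good above neither). A score that is at least as good as some good score must have expansion 3 to 6, inner cell mass A or B and trophectoderm A or B. There are 4 × 2 × 2 = 16 such scores, and 6 + 8 = 14 of them are classified. The two left over are 3AA and 3AB.

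| Unclassified score | Good score it beats | Better on | Equal on |
|---|---|---|---|
| 3AA | 3BA | inner cell mass | expansion, trophectoderm |
| 3AA | 3BB | inner cell mass, trophectoderm | expansion |
| 3AB | 3BB | inner cell mass | expansion, trophectoderm |

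That makes 3 inverted pairs. 3AB against 3BA is not counted: each is better on one scale, so the protocol does not order them. No pair is inverted between excellent and good. A full enumeration of the 64 scores by program gave the same counts and the same three pairs.

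**Counts with good redefined** as expansion 3 to 6, inner cell mass A or B, trophectoderm A or B, and not excellent.

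- Excellent: 6, unchanged.
- Good: 16 − 6 = 10.
- Other: 64 − 6 − 10 = 48.
- Inverted pairs: 0. Any score at least as good as an excellent one is excellent, and any score at least as good as a good one is now good or excellent.

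**Where the current rule shows.** It affects the count and percentage of good-quality blastocysts, the best-blastocyst summary (Protocol 9.6.3, SAP 9.3.10), and the overall-quality summary in SAP 9.3.9 where that uses these classes. The SAP 9.2.1 breakdown is affected only if its levels are these classes.

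**The case against.** The strongest reply is that little depends on this. The main presentation of blastocyst quality is the frequency distribution of the three component grades, where 3AA and 3AB are fully counted. The only class that 7.2.9 itself calls a secondary endpoint is excellent, which is untouched. The remaining summaries are descriptive, with no test or decision rule. Two labels out of 64 say nothing about how many blastocysts carry them. All of this stands, and it limits the importance of the point.

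The ranking of excellent above good above unclassified is nowhere stated. It does follow from the labels and grade descriptions, and no passage gives a reason for dropping a blastocyst from good because its inner cell mass is better. The biopsy rule in the same section treats inner cell mass A and B alike at expansion 3 to 6.

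The subject-level effect may be narrower than it first appears. For a woman with both a 3AA and a 3BB, the result depends on whether best means best morphology or best class, which the documents leave open. This also stands. But when her best blastocyst is 3AA under whichever meaning is used, she falls in neither category.

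Narrowing good to expansion 4 to 6 would also remove all three inversions. It would do so by taking 3BA and 3BB out of a class in which the protocol now counts them. The sponsor has to confirm what was intended; widening good is the smaller change.

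The table shells are in a separate document that was not available and may already carry a residual row or named levels. They would not correct the protocol's definition.

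**Conclusion.** The concern holds. Read literally, Protocol 7.2.9 places 3AA and 3AB below 3BB, and 3AA below 3BA, and nothing later in the protocol or SAP repairs this. The size is 3 inverted pairs, all arising from 2 of the 64 score labels. These are counts of labels, not of blastocysts; without a frequency for 3AA and 3AB, the effect on the trial's tables cannot be computed. The conclusion rests on A being better than B on both letter scales and on good ranking above unclassified.

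It is a minor point, worth correcting because it is cheap. Sample size, significance level and the primary analysis do not depend on it.

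**What to change.** Before database lock:

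1. In SAP 9.3.9 and 9.3.10, define good quality for analysis as expansion 3 to 6, inner cell mass A or B, trophectoderm A or B, and not excellent. Report all remaining blastocysts in a stated residual category, other. The sponsor should confirm that this is the intended class.
2. State in SAP 9.3.10 how a woman's best blastocyst is chosen when she has several.
3. Apply the same classes to the Day 6 and Day 7 grading, which Protocol 7.2.10 ties to 7.2.9.
4. If the SAP 9.2.1 breakdown by quality of the transferred blastocyst uses these classes, list its levels there, including the residual one.
5. Record the change in SAP section 12.

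The class correction costs one line in the SAP and one derivation in the programs; the best-blastocyst rule adds a sentence. The component grades are already recorded in the eCRF, so no new data are needed. The change concerns analysis classes only and leaves the choice of blastocyst for transfer or biopsy as it is.
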